PPD/QuantIFERON-TB Gold (per local guidelines)	X							Subjects will return 2 to 3 days after Visit 1 to have their PPD test read.
ECGs	X						X	This should be completed prior to any study dose administration or blood draw. Subjects should be supine for approximately 5 to 10 minutes before ECG collection and remain supine but awake during ECG collection.
C-SSRS	X	X	X	X	X	X	X	
CCI [REDACTED]		■	■	■	■	■	■	[REDACTED]
Study drug dosed		X			X		X	At Week 16, subjects will only receive study drug dosing if PASI <90.

Induction Dosing Period (Visits 1-7)								
Visit No.	V1	V2	V3	V4	V5	V6	V7	Comments
Week Relative to Study Drug Start	-4	0	2	4	8	12	16	All activities should be completed prior to any study dose administration unless otherwise stated below.
Day with Visit Tolerance Interval	≤28 from V2	0	14 ± 2	28 ± 3	56 ± 5	84 ± 5	112 ± 5	Visit 1 procedures may be conducted over more than 1 day as long as all tasks are completed within the allowable visit tolerance (at least 3 days should be allowed for receipt of laboratory test results).
Clinical Efficacy								
PASI	X	X	X	X	X	X	X	
sPGA	X	X	X	X	X	X	X	
PSSI, if applicable		X	X	X	X	X	X	Once a subject experiences symptoms related to scalp involvement, this form should be completed at all remaining indicated visits.
Whole body photographs		X					X	If subject has agreed to whole body photographs.
Health Outcomes								
PSS	Electronic Diary Taken Daily from Screening (V1) up to Week 16 (V7)						X	
PatGA		X	X	X	X	X	X	
DLQI		X	X	X	X	X	X	
SF-36		X					X	
Laboratory Tests								
Hematology	X	X	X	X	X	X	X	Unscheduled blood chemistry and hematology panels may be performed at the discretion of the investigator.
Lymphocyte subsets		X					X	
Serum chemistry	X	X	X	X	X	X	X	Unscheduled blood chemistry and hematology panels may be performed at the discretion of the investigator.
Urinalysis	X	X			X		X	

Induction Dosing Period (Visits 1-7)								
Visit No.	V1	V2	V3	V4	V5	V6	V7	Comments
Week Relative to Study Drug Start	-4	0	2	4	8	12	16	All activities should be completed prior to any study dose administration unless otherwise stated below.
Day with Visit Tolerance Interval	≤28 from V2	0	14 ± 2	28 ± 3	56 ± 5	84 ± 5	112 ± 5	Visit 1 procedures may be conducted over more than 1 day as long as all tasks are completed within the allowable visit tolerance (at least 3 days should be allowed for receipt of laboratory test results).
HBsAg, HBcAb, HBsAb	X							

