6.1.1. Subject Populations for Analyses

For purposes of analysis, populations for analyses are described in [Table 6.1](#).

Table 6.1. Subject Populations for Analyses

Population	Description
Intent-to-treat (ITT) (Induction Period Efficacy)	All randomized subjects, even if the subject does not take the assigned treatment, does not receive the correct treatment, or otherwise does not follow the protocol: 
 Unless otherwise noted, efficacy and health outcomes analyses for the Induction Period will be conducted on this population. Subjects will be analyzed according to the treatment to which they were assigned.
Induction Period Safety	All randomized subjects who received at least 1 dose of study treatment: 
 Unless otherwise noted, safety analyses for the Induction Period will be conducted on this population. Subjects will be analyzed according to the treatment to which they were assigned.
Maintenance Period Efficacy	All randomized subjects who have entered the Maintenance Period (see definition of entering Maintenance Period in Section 6.1.2.1): 
 Unless otherwise noted, efficacy, and health outcomes for the Maintenance Period will be conducted on this population. Subjects will be analyzed according to the treatment to which they were assigned in Maintenance Period.

Population	Description
Maintenance Period Safety	
All randomized subjects received at least 1 dose of study treatment who have entered the Maintenance Period (see definition of entering Maintenance Period in Section 6.1.2.1):
 
 • Unless otherwise noted, safety analyses for the Maintenance Period will be conducted on this population. • Subjects will be analyzed according to the treatment to which they were assigned in Maintenance Period, with all LY3074828 300 mg Q8W arms combined, that is, there will be 4 treatment groups in the Maintenance Period: 
 ○ LY 300 mg PRN ○ LY 100 mg PRN ○ LY 30 mg PRN ○ LY 300 mg Q8W (including subjects from 4 Induction Period treatment groups)

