6.3. Handling of Dropouts or Missing Data

6.3.1. Non-Responder Imputation (NRI)

Analysis of categorical efficacy and health outcome variables will be assessed using a NRI method. Subjects will be considered a non-responder for the NRI analysis if they do not meet the clinical response criteria or have missing clinical response data at the analysis time point. Randomized subjects without at least 1 postbaseline observation will also be defined as non-responders for the NRI analysis.

Due to the design, PRN subjects who got rescued will get a different treatment (300 mg LY SC Q8W), therefore the subsequent visits following the first dose of rescue treatment will be defined as non-responders in the analysis for the Maintenance Period.

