PSSI	Psoriasis Scalp Severity Index (PSSI): will be used if the patient has scalp psoriasis at baseline. The scalp will be assessed for erythema (redness), induration (hardness), and desquamation (shedding of skin) and percentage of area affected as follows: Erythema, Induration and Desquamation: 0 = Absent 1 = Slight 2 = Moderate 3 = Severe 4 = Severest Possible Percent of Scalp Involved: 0 = none 1 = <10% 2 = 10 – 29% 3 = 30 – 49% 4 = 50 – 69% 5 = 70 – 89% 6 = 90 – 100%	PSSI score	The PSSI score is a composite score derived from the sum of the scores for erythema, induration and desquamation multiplied by the score for the extent of scalp area involved (percent of scalp involved). The range is 0 to 72.	If any individual score is missing, the PSSI score will not be calculated, hence missing.
		PSSI improvement from baseline and percent change from baseline (for subjects with baseline scalp psoriasis involvement only)	Calculated as: observed PSSI – baseline PSSI	Missing if baseline or observed value is missing
		PSSI score =0	A PSSI response is defined as a PSSI score of 0, which is also referred to as scalp clearance.	Missing if PSSI score is missing
DLQI	Dermatology Life Quality Index (DLQI): is a validated, dermatology-specific, patient-reported measure that evaluates patient’s health-related quality of life. This questionnaire has 10 items that are grouped in 6 domains, including symptoms and feelings, daily activities, leisure, work and school, personal relationships, and treatment. The recall period of this scale is over the “last week”. Response categories and corresponding scores are:	DLQI symptoms and feelings domain	Sum of responses of questions #1 and #2: #1. How itchy, sore, painful or stinging has your skin been? #2. How embarrassed or self-conscious have you been because of your skin?	If 1 question in a domain is missing, that domain is missing.
		DLQI daily activities domain	Sum of responses of questions #3 and #4: #3. How much has your skin interfered with you going shopping or looking after your home or garden? #4. How much has your skin influenced the clothes you wear?	If 1 question in a domain is missing, that domain is missing.

Measure	Description	Variable	Derivation / Comment	Imputation Approach if with Missing Components

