	Time to first loss of response (PASI 90, PASI 100) for PRN subjects	KM product limit curve; time to loss of response	Maintenance Period Efficacy Population	Maintenance Period

Measure	Variable	Analysis Method (Sections 6.1.3)	Population (Section 6.1.1)	Time Point
	Time to recapture of response (PASI 90, PASI 100) after first loss of response for PRN subjects	KM product limit curve; time to response recapture after first loss of response	Maintenance Period Efficacy Population	Maintenance Period
	Time to recapture of response (PASI 50, PASI 90) after loss of response for rescued subjects	KM product limit curve; time to response recapture after first loss of response	Rescue Period Efficacy Population	Rescue Period
sPGA	sPGA (0,1); sPGA (0)	Logistic regression analysis with NRI	ITT Population	All pairwise comparisons against placebo at all postbaseline visits in Induction Period
		Summary statistics with NRI	Maintenance Period Efficacy Population	All visits in Maintenance Period
		Summary statistics (As observed) or individual trajectory line plot if total number of subjects is too small	Rescue Period Efficacy Population	All visits in Rescue Period
BSA	BSA change from baseline	MMRM; mBOCF ANCOVA	ITT Population	All pairwise comparisons against placebo at all postbaseline visits in Induction Period
		MMRM	Maintenance Period Efficacy Population	All visits in Maintenance Period
PSSI	PSSI percent improvement from baseline (for subjects with scalp psoriasis involvement only); PSSI score (for all subjects)	MMRM; mBOCF ANCOVA	ITT Population	All pairwise comparisons against placebo at all postbaseline visits in Induction Period
		MMRM	Maintenance Period Efficacy Population	All visits in Maintenance Period
	PSSI score = 0 (for all subjects)	Logistic regression analysis with NRI	ITT Population	All pairwise comparisons against placebo at all postbaseline visits in Induction Period
	Summary statistics with NRI	Maintenance Period Efficacy Population	All visits in Maintenance Period	

Measure	Variable	Analysis Method (Sections 6.1.3)	Population (Section 6.1.1)	Time Point
DLQI	DLQI (0,1), DLQI (0)	Logistic regression analysis with NRI	ITT Population	All pairwise comparisons against placebo at all postbaseline visits in Induction Period
		Summary statistics with NRI	Maintenance Period Efficacy Population	All visits in Maintenance Period

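### As written, the SAP counts a subject who never had scalp psoriasis as a scalp-clearance failure (PSSI = 0), and its PSSI percent-change formula does not give a percentage

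*SAP*

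**What the plan says.** **Endpoint and population.** SAP Table 6.3 (Section 6.9) lists "PSSI score = 0 (for all subjects" for logistic regression with NRI in the ITT population at every induction visit, and for NRI summaries in the Maintenance Period. The continuous row reads "PSSI percent improvement from baseline (for subjects with scalp psoriasis involvement only); PSSI score (for all subjects". SAP Table 6.1 defines ITT as "All randomized subjects, even if the subject does not take the assigned treatment", with no scalp criterion.

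**Who has a PSSI.** SAP Table 6.2 says that the index "will be used if the patient has scalp psoriasis at baseline". The Protocol Schedule of Activities marks the PSSI as applicable only to some subjects and says: "Once a subject experiences symptoms related to scalp involvement, this form should be completed at all remaining indicated visits". Protocol 9.1.3 likewise starts PSSI scoring when scalp psoriasis appears at any time during the study. SAP 6.6 tabulates baseline PSSI for subjects with scalp disease at baseline or with later onset, and records scalp psoriasis as yes or no on an eCRF form. Scalp disease is not an inclusion criterion in Protocol 6.1.

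**Missing data.** Table 6.2 defines response as a PSSI of 0, calls it scalp clearance, and gives the rule "Missing if PSSI score is missing". SAP 6.3.1 makes non-responders of subjects who "have missing clinical response data at the analysis time point".

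**Formula.** For PSSI improvement and percent change alike, Table 6.2 gives observed minus baseline.

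**The concern.** Clearance means something only for a scalp that was affected. Under the written rules a never-affected scalp sits in the denominator as a failure at every visit, in every arm. The reported rates then mix drug effect with the share of enrolled subjects who had scalp disease. SAP 6.1.3 has both odds ratios and treatment differences reported, and both shrink with that share. A reader comparing these figures with a trial that analyses affected subjects only would see a smaller effect for a reason unrelated to the drug.

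The formula is a second, independent defect. A program that followed Table 6.2 would report an absolute change under a percentage label, with the sign reversed relative to PASI in the same table.

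**Working it through.** The plan gives no figure for PSSI, so there is none to reproduce. The check is the chain of rules, followed by an illustration of its size.

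**1. Rule chain for a subject with no scalp disease**

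| Step | Source | Result |
|---|---|---|
| PSSI form completed? | Protocol Section 2 and 9.1.3; SAP Table 6.2 | No |
| PSSI score | SAP Table 6.2 | Missing |
| PSSI = 0 response | SAP Table 6.2 | Missing |
| In the analysis set? | SAP Tables 6.1 and 6.3 | Yes (ITT) |
| NRI | SAP 6.3.1 | Non-responder |

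The continuous PSSI score carries the same all-subjects label but behaves differently. The MMRM and ANCOVA include baseline value (SAP 6.1.3), so a subject with no baseline PSSI cannot enter. The two analyses therefore have different effective populations.

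**2. Size**

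Let s be scalp prevalence, and p1 and p0 the clearance rates among affected subjects (LY3074828 and placebo). All three are assumptions. Never-affected subjects count as failures, so:

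- reported rates = s·p1 and s·p0
- reported difference = s·(p1 − p0)
- reported odds ratio (OR) = [s·p1/(1 − s·p1)] / [s·p0/(1 − s·p0)]

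For s = 0.75, p1 = 0.70 and p0 = 0.08:

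- rates: 0.75 × 0.70 = 52.5% and 0.75 × 0.08 = 6.0%; difference 46.5 points
- OR: (0.525/0.475)/(0.060/0.940) = 17.3
- among affected subjects: difference 62 points; OR (0.70/0.30)/(0.08/0.92) = 26.8

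| p1 vs p0 | OR, affected | s = 90%: difference, OR | s = 75%: difference, OR | s = 60%: difference, OR |
|---|---|---|---|---|
| 50% vs 3% | 32.3 | 42.3 pts, 29.5 | 35.3 pts, 26.1 | 28.2 pts, 23.4 |
| 70% vs 8% | 26.8 | 55.8 pts, 21.9 | 46.5 pts, 17.3 | 37.2 pts, 14.4 |
| 80% vs 15% | 22.7 | 58.5 pts, 16.5 | 48.8 pts, 11.8 | 39.0 pts, 9.3 |

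**3. Power**

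This uses the exact two-sided Fisher test at 0.05, standing in for the Firth logistic model, with 50 per arm under the written rule and 45, 38 or 30 per arm when restricted. In all nine scenarios power is at least 98.3% as written and at least 99.4% restricted. For a weaker assumed effect (30% vs 8%), power restricted versus as written is 69.6% vs 68.6% at 90% prevalence, 62.0% vs 56.0% at 75%, and 46.7% vs 41.5% at 60%. The loss is 1 to 6 points.

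**4. Formula**

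The PSSI runs from 0 to 72. A subject going from 72 to 0 gets 0 − 72 = −72 under Table 6.2. The PASI form, 100 × (baseline − observed)/baseline, gives 100 × (72 − 0)/72 = 100.

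**The case against.** **The all-subjects label looks deliberate.** Table 6.3 separates it from percent improvement, which is limited to scalp subjects. That is fair, and restriction does change the stated population. But the contrast does not make a never-affected scalp a treatment failure, and the endpoint is still called clearance.

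**The denominator is partly disclosed.** SAP 6.1 requires categorical summaries to show how many patients provided data, and SAP 6.6 tabulates scalp status. A reader could rescale: 52.5/0.75 = 70% and 6.0/0.75 = 8%. This stands as mitigation. It is only approximate once there is dropout or later onset, and it does not recover the model-based odds ratio or its interval.

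**A reader might infer that uncompleted forms are scored 0.** The scale has a zero level ("0 = Absent 1 = Slight 2 = Moderate"), and SAP 6.6 tabulates a baseline PSSI for subjects with later onset. Never-affected subjects would then be responders from the first visit: 77.5% versus 31.0% and OR 7.7 in the worked example, with power as low as 77.7% in the nine scenarios. No visible passage assigns 0 to a form that was not completed, and the written chain gives non-response. Neither the power loss nor a claim that the SAP has no rule is supported.

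**Some related points are softer than they look.** Table 6.2 limits percent improvement to baseline scalp involvement, so the zero denominator that later onset could produce arises only if Table 6.3, which omits the word baseline, is read alone. Table 6.2 ties PSSI use to baseline disease without saying only, so its difference from Protocol 9.1.3 needs reconciling but is not a flat contradiction.

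**Conclusion.** The point holds and is minor. The written rules score never-affected subjects as not cleared, which dilutes the reported rates, differences and odds ratios by scalp prevalence. In the scenarios above the odds ratio falls from 22.7–32.3 among affected subjects to 9.3–29.5. Those sizes rest on assumed prevalence and clearance, and they ignore model covariates and scalp disease that starts after baseline. The formula error rests on no assumption.

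A reader might infer bias towards one arm or a false-positive risk. The documents do not support either: the rule is the same in every arm, randomization balances scalp status in expectation, and type I error is not inflated. PSSI is exploratory (SAP 4.3 and 6.9.3), a scalp-restricted percent-improvement analysis is also planned, and the primary and secondary analyses are untouched.

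One limit remains. Protocol 10.3.3.3 (exploratory analyses) appears in the contents list, but the text at that place is blacked out, and the protocol's objectives table is not visible. A scoring rule may exist there. SAP 6.9.3 nevertheless sends the PSSI analyses to Tables 6.2 and 6.3, which are visible.

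**What to change.** - Restrict the PSSI = 0 (NRI) and PSSI score (MMRM and mBOCF ANCOVA) analyses, and the matching Maintenance Period summaries, to subjects with scalp psoriasis at baseline, meaning eCRF flag yes or baseline PSSI > 0.
- Keep flagged subjects with a missing PSSI in the PSSI = 0 denominator as non-responders. Baseline PSSI > 0 alone would drop affected subjects whose baseline form is missing.
- Summarise scalp disease that starts after baseline separately.
- Reconcile SAP Table 6.2 with Protocol 9.1.3 and SAP 6.6 on who is scored.
- Define PSSI percent improvement as 100 × (baseline − observed)/baseline for subjects with baseline PSSI > 0, and carry the word baseline into the Table 6.3 restriction.

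The cost is table wording, one formula and a subset built from data already collected. The downside is a smaller n for this exploratory endpoint: at an assumed 75% prevalence, 0.75 × 50 = 37.5, or about 38 per arm instead of 50.

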6.9.1. Primary Outcome and Methodology

Primary outcome Psoriasis Area and Severity Index (PASI) 90 and its analysis are described in [Table 6.2](#) and [Table 6.3](#).

6.9.2. Secondary Efficacy Analyses

Analyses of PASI and Static Physician Global Assessment (sPGA) secondary outcomes are described in [Table 6.2](#) and [Table 6.3](#).

6.9.3. Exploratory Analyses

Analyses of body surface area (BSA) and Psoriasis Scalp Severity Index (PSSI) exploratory outcomes are described in [Table 6.2](#) and [Table 6.3](#).

The Kaplan-Meier product limit method will be used to estimate the survival curves for the Maintenance and Rescue Period time-to-event variables (time to loss of response for subjects in as needed (PRN) arm, time to response recapture after loss of response for subjects who lost response in PRN arm). Time to event analyses will be summarized by PRN treatment arms.

Summary of PRN doses, including total number of PRN doses given and week of first PRN dose given after loss of response, will be summarized by PRN treatment arms.

6.10. Health Outcomes/Quality-of-Life Analyses

Analyses of Psoriasis Symptoms Scales (PSS), Global Assessment Dermatology Life Quality Index (DLQI), Patients Global Assessment of Psoriasis (PatGA), and SF-36 health outcomes are described in [Table 6.2](#) and [Table 6.3](#).

6.11. Pharmacokinetic/Pharmacodynamic Methods

Details of pharmacokinetic/pharmacodynamic (PK/PD) analyses can be found in a separate PK/PD analysis plan.

6.12. Safety Analyses

All safety evaluations will be based upon the Safety Population as defined in Section [6.1.1](#).

Safety and tolerability will be evaluated in terms of adverse events (AEs), treatment-emergent AEs (TEAEs), discontinuations due to AEs, deaths, other SAEs, permanent discontinuations and interruptions of study drug, laboratory analyses including neutrophil counts and immunogenicity, Columbia Suicide Severity Rating Scale (C-SSRS), vital signs, echocardiogram (ECG) findings, and concomitant medications.

The Induction Period safety analyses will summarize each LY3074828 dose regimen (300 mg, 100 mg, and 30 mg) and compare the pooled LY3074828 dose regimens to placebo. Treatment group comparisons will be analyzed using the methods described in Section [6.1.3](#).

For the Maintenance Period, safety will be summarized by treatment (each PRN arm and 300 mg Q8W). No comparisons will be conducted. Only events occurred in the Maintenance Period will be included in this analysis, that is, no events in the Rescue Period will be included. Only a

smaller set of safety analyses (for example, TEAE, serious adverse events (SAE), AE leading to study treatment discontinuation, TE high/low labs, TE high/low vitals) will be needed for the Maintenance Period.

In addition, an overall summary of safety for all LY3074828 exposed subjects, will be provided by presenting all LY3074528 arms pooled including the Induction, Maintenance, and Rescue Periods; Follow-Up Period separately (if there are meaningful number of subjects); and All Periods + Follow-up Period. Only a smaller set of safety analyses (for example, TEAE, SAE, AE leading to study treatment discontinuation, TE high/low labs, TE high/low vitals) will be needed for the overall safety summary.

Safety event occurring on the same day of the end of a period and the start of next period will be counted towards the next period, for example, if a safety event occurred on the date of PASI measurement at Week 16, the event will be allocated to the Maintenance Period.

Change from baseline analyses will use baseline definition provided in Section 6.1.2.

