#### **10.3.1.1. General Considerations for Analyses in the Induction Period**

Continuous data will be summarized in terms of the mean, standard deviation, minimum, maximum, median, and number of observations. Categorical data will be summarized as frequency counts and percentages. Comparisons between each LY3074828 dose regimen (30 mg, 100 mg, 300 mg) and placebo will be performed for all analyses in the induction period with no adjustment for multiple comparisons.

For the induction period efficacy, health outcomes, and safety analyses, baseline is defined as the last available value before the initial randomization, which in most cases will be the measure recorded at Week 0 (Visit 2). Change from baseline will be calculated as the visit value of interest minus the baseline value.

Treatment comparisons of categorical efficacy variables will be conducted using a logistic regression analysis with treatment, geographic region (US/Non-US), and prior exposure to biologic therapy use (yes/no) in the model. The proportions and 95% confidence intervals will be reported.

Treatment comparisons of continuous efficacy and health outcome variables will be made using mixed-effects for repeated measures (MMRM).

When MMRM is used, the model includes treatment, geographic region (US/Non-US), prior exposure to biologic therapy use (yes/no), baseline value, visit, and the interaction of treatment-by-visit as fixed factors. The covariance structure to model the within-subject errors will be unstructured. If the unstructured covariance matrix results in a lack of convergence, the heterogeneous Toeplitz covariance structure, followed by the heterogeneous autoregressive covariance structure will be used. The Kenward-Roger method will be used to estimate the denominator degrees of freedom. Type III sums of squares for the least squares means will be used for the statistical comparison; the 95% confidence interval will also be reported. Treatment group comparisons with placebo at Week 16 (Visit 7) and all other visits will be tested.

Fisher's exact test will be used for categorical safety data including AE, baseline, and discontinuations. Continuous vital sign and laboratory values will be analyzed by analysis of covariance (ANCOVA) with treatment and baseline value in the model. Other continuous safety variables will be analyzed by t-tests, unless otherwise stated.

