**10.3.4. Safety Analyses**

Safety will be assessed by evaluating AE, laboratory analytes, vital signs, ECGs, and C-SSRS.

The induction period safety analyses will compare LY3074828 to placebo for which treatment group comparisons will be analyzed using the methods described in Section 10.3.1.1. The maintenance period safety analyses will summarize safety measures by treatment. Summaries of safety data collected during the follow-up period will be presented separately.

AEs will be coded according to the *Medical Dictionary for Regulatory Activities* and summarized by system organ class, preferred term, severity, and relationship to investigational product. A treatment-emergent adverse event (TEAE) is defined as an event that first occurred or worsened in severity after baseline. For each event classification term, the number of subjects experiencing a TEAE with that classification term will be tabulated.

Treatment-related TEAEs are defined as events that are indicated by the investigator on the eCRF to be related to treatment. If a subject reports the occurrence of a particular event more than once, the most severe of those events will be included in the summary tables of TEAEs, and the most severe of the most related of those events will be included in the summary tables of

treatment-related events. For events that are gender specific, the denominator and computation of the percentage will only include subjects from the given gender.

Additional safety parameters include laboratory analytes, vital signs, ECGs, and C-SSRS. Laboratory analytes and vital signs will be presented as mean changes from baseline and as incidence of abnormal values. ECG and C-SSRS data will be listed by subject. Other covariate data, including body weight, will be summarized by treatment group.

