5.2. Determination of Sample Size

Approximately 200 subjects will be randomized at a 1:1:1:1 ratio in the blinded induction dosing period to LY3074828 30 mg, 100 mg, 300 mg, and placebo (50 subjects per dosing regimen, respectively). Randomization will be stratified by prior exposure to biologic therapy for psoriasis (yes/no).

Assuming 60% and 3% PASI 90 response rates at 16 weeks for LY3074828 and placebo, respectively, pairwise comparisons to placebo have over 99% power using a 2-sided Fisher's exact test at the 0.05 significance level, with no adjustment for multiple comparisons.

As results for PRN dose arms in the Maintenance Period will support the maintenance dosing strategy in Phase 3 planning, a reasonable total number of subjects who completed 1-3 visits in the Maintenance Period (Week 20 to Week 28) will be needed. Based on study simulations under the treatment effect scenario outlined above, approximately 49 subjects (9 on 30 mg, 18 on 100 mg, 22 on 300 mg PRN arms) will have completed the Week 20 visit at the time of the primary endpoint datalock.

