- If a partial AE start date is present, the date will be compared as far as possible to the date of Visit 29 or ETV in order to determine whether the event is follow-up emergent or not. If there is any doubt, the event will be flagged as follow-up emergent, unless the same event was already counted as treatment-emergent during the Induction Period.

Adverse events and TEAEs will be summarized and analyzed for the safety population for the Induction Period. Treatment comparisons between all Induction Period LY3074828 dose regimens (300 mg, 100 mg, 30 mg) combined and placebo will be conducted using Fisher's exact test. Resulting p-values will be used to help identify potential adverse drug reactions. Significant p-values will need to be interpreted with caution due to the fact that multiplicity is not controlled in this study.

Maintenance Period adverse events and TEAEs will be summarized by treatment. Follow-up emergent adverse events and TEAEs during the Rescue Period will be summarized in the All Periods safety analyses.

Additionally,

- An overall summary of AEs including the number and percentage of patients who experienced TEAE, TEAE by maximum severity, death, SAE, discontinuations from the treatment due to an AE, and TEAEs of special interest.
- TEAE by system organ class (SOC) and PT.
- TEAEs related to study treatment by SOC and PT
- TEAE by maximum severity, SOC, and PT.

If a safety event occurred on the same date of the last date of Induction and the first date of the Maintenance Period, the event will be allocated to the Maintenance Period only.

If a safety event occurred on the same date of the last date of Maintenance and the first date of Rescue, compare the event onset time with rescue dose time to allocate the event to the Maintenance Period or Rescue Period accordingly; if either time is missing, the event will be allocated to the Rescue Period only.

If a safety event occurred on the same date of the last date of Maintenance or Rescue and the first date of the Follow-up Period, the event will be allocated to the previous period (Maintenance or Rescue) only.

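### The SAP tests induction adverse events only for the pooled LY3074828 doses against placebo, where the protocol specifies each dose against placebo, and it does not explain the change

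*SAP*

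**What the plan says.** Protocol 10.3.1.1 sets the rule for induction: "Comparisons between each LY3074828 dose regimen (30 mg, 100 mg, 300 mg) and placebo will be performed for all analyses in the induction period", without multiplicity adjustment. The same section names Fisher's exact test for adverse events. Protocol 10.3.4 speaks of comparing LY3074828 with placebo in induction and adds that "treatment group comparisons will be analyzed using the methods described in Section 10.3.1.1".

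SAP 6.12 summarizes each dose for the induction period, but the comparison it plans is to "compare the pooled LY3074828 dose regimens to placebo". SAP 6.12.2 repeats this for adverse events and treatment-emergent adverse events (TEAEs): comparisons between all Induction Period "dose regimens (300 mg, 100 mg, 30 mg) combined and placebo will be conducted using" Fisher's exact test. It gives the tests a purpose: "Resulting p-values will be used to help identify potential adverse drug reactions". It also warns that significant p-values need caution because multiplicity is not controlled.

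SAP 6.1.3 names Fisher's exact test for adverse events and adds no dose-level contrast. For efficacy, the same section does compare each dose with placebo. The SAP neither mentions nor justifies the different choice for safety.

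**The concern.** The study randomizes to doses that span tenfold, from 30 mg to 300 mg, and its safety findings are meant to support Phase 3 design (Protocol 3.1). If an adverse reaction occurs mainly at the top dose, a pooled test averages it with two arms that carry little or none of it.

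Induction is also the only placebo-controlled part of the study. At Week 16 all placebo subjects move to LY3074828, and SAP 6.12 plans no comparisons for the maintenance period. A dose-against-placebo test that is not done in induction has no later counterpart.

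**Working it through.** **Inputs.** SAP 5.2: "Approximately 200 subjects will be randomized at a 1:1:1:1 ratio in the blinded induction dosing period", with 50 per arm, so the pooled group has 3 × 50 = 150. Test: two-sided Fisher's exact at 0.05. Adverse event rates are assumptions, because the documents give none.

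**The plan's own figure.** SAP 5.2 states over 99% power for PASI 90 at 60% against 3%, 50 per arm, with Fisher's exact test. Exact enumeration gives more than 99.99%, so the figure reproduces. No power is stated for safety.

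**Formulas.** Power is the sum of P(X = x) × P(Y = y) over all pairs (x, y) for which Fisher's p ≤ 0.05.
- X, placebo: Bin(50, p0).
- Y, 300 mg alone: Bin(50, p300).
- Y, pooled: the sum of independent Bin(50, p30), Bin(50, p100) and Bin(50, p300) counts.
- Pooled rate: (p30 + p100 + p300)/3.

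**Results with 4% on placebo.**

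| Rate at 30/100/300 mg (%) | Pooled rate (%) | Pooled risk difference (points) | Power, 300 mg vs placebo | Power, pooled vs placebo |
|---|---|---|---|---|
| 4/4/24 | 10.7 | 6.7 | 78% | 25% |
| 4/10/24 | 12.7 | 8.7 | 78% | 40% |
| 4/14/24 | 14.0 | 10.0 | 78% | 50% |
| 8/14/24 | 15.3 | 11.3 | 78% | 60% |
| 8/16/24 | 16.0 | 12.0 | 78% | 64% |
| 10/17/24 | 17.0 | 13.0 | 78% | 70% |
| 24/24/24 | 24.0 | 20.0 | 78% | 95% |
| 4/4/30 | 12.7 | 8.7 | 93% | 40% |

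**Other assumed rates, excess at 300 mg only (300 mg test, then pooled test).**
- 2% against 15%: 51%, 9%.
- 5% against 25%: 75%, 23%.
- 10% against 30%: 64%, 16%.
- 10% against 40%: 93%, 32%.

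**What is diluted.** In the first row of the table the risk difference falls from 20 points to 20/3 = 6.7, exactly threefold. The test statistic falls less, because the pooled group is larger:
- 300 mg: z = 0.20/√(0.04×0.96/50 + 0.24×0.76/50) = 0.20/0.0665 = 3.01.
- Pooled: z = 0.0667/√(0.04×0.96/50 + 50×(2×0.04×0.96 + 0.24×0.76)/150²) = 0.0667/0.0367 = 1.82.
- Ratio: 3.01/1.82, about 1.7.

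**In counts.** With 0/50 on placebo and 6/50 on 300 mg, Fisher's p = 0.027. If the lower doses have no events, the pooled comparison is 6/150 against 0/50, and p = 0.34.

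**The case against.** **Dose-level safety is not hidden.** A reader might infer that a top-dose signal would go unseen. The documents do not support that. SAP 6.12 summarizes each dose, SAP 6.12.2 presents adverse event counts and percentages by dosing regimen, and SAP 6.12.2.1 gives common events by treatment. The p-values only help to identify reactions. A large excess would show in these tables without a test. This stands.

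**Pooling is not weak for all dose-related harm.** The 25% figure needs no excess at 100 mg, which is the extreme case. With graded risk the loss against the 300 mg test is 8 to 38 points in the rows shown (78% against 70% down to 40%). With equal risk at every dose, pooling is clearly better: 95% against 78%, or 76% against 51% at 5% on placebo and 20% on every dose. This stands, and it is why the pooled test should stay.

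**The added tests do little for modest effects.** With 4% elsewhere, a 300 mg rate of 10% or 12% gives the 300 mg test only 9% or 17% power, although the pooled test has 3% or 5%. This stands.

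**The protocol may leave room.** Section 10.3.4, read alone, could mean a pooled comparison, but its reference to 10.3.1.1 favours the dose-level reading. Section 10.3.1 allows changes to non-principal methods without an amendment, provided that the clinical study report describes and justifies them. So it would be too strong to call pooling impermissible. What remains is that the SAP gives no reason for the change.

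**Conclusion.** The point holds as an unexplained mismatch between protocol and SAP that removes the dose-level adverse event test while leaving the dose-level tables in place. The current protocol text (21 August 2018) is later than SAP Version 2 (28 June 2017) and still carries the dose-level rule, so the two now disagree.

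The effect depends on the shape of the dose-response for harm. At 4% on placebo and 24% on 300 mg, the pooled test has 25%, 40% to 64%, or 95% power for an excess at 300 mg only, for the graded cases from 4/10% to 8/16% at 30/100 mg, and for a shared excess. The 300 mg test has 78% throughout. These figures rest on assumed rates and 50 treated subjects per arm.

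A reader might take from this that pooling weakens any safety signal threefold. That factor applies only to the risk difference, with equal arms and no excess at the two lower doses. It does not apply to the test statistic, the p-value or the relative risk. The point concerns adverse events; the laboratory shift tests in SAP 6.12.4 do not name their contrast. The primary endpoint and the efficacy analyses are unaffected.

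**What to change.** In SAP 6.12 and 6.12.2, keep the pooled comparison and add unadjusted Fisher's exact tests of 30 mg, 100 mg and 300 mg against placebo for induction TEAEs, as Protocol 10.3.1.1 states. If the sponsor prefers the pooled test alone, the SAP should say that this departs from the protocol and why, and the clinical study report should repeat it.

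The cost is three more nominal p-values per event term and no new data. Under no effect, three independent tests at a full 5% would give at least one false signal with probability 1 − 0.95³ = 14.3% per term. The shared placebo arm and the conservatism of Fisher's test for rare events should keep the true figure lower. The caution already in SAP 6.12.2 should be extended to these columns.
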